6.1 Overview of study Design

The study is a multicenter, blinded, non-matching placebo-controlled, randomized clinical trial to evaluate the superiority of active therapy (lopinavir/ritonavir) versus placebo control. Patients, treating clinicians, and study personnel are blinded to study group assignment. Randomization uses permuted blocks and is stratified by site and age (≥ 65 years or < 65 years) in a 1:1 ratio through a central electronic system. The primary outcome, measured from Study Day 1 (receipt of study drug) to Study Day 15, is a seven-level ordinal scale describing the patient's clinical status defined in Section 5. The planned analysis is a longitudinal Bayesian proportional odds model with a skeptical prior, and is powered to detect an odds ratio of greater than 1.75.

6.2 Inclusion-Exclusion Criteria and General Study Population

Patients aged ≥ 18 years who have laboratory-confirmed SARS-CoV-2 infection by RT-PCR or other molecular test within the past 6 days, whose symptoms began ≤ 6 days previously, and who currently remain with at least one symptom are eligible to participate. Qualifying symptoms are cough, fever, shortness of breath, chest pain, abdominal pain, nausea/vomiting, diarrhea, body aches, weakness/fatigue.

Detailed exclusion criteria are listed in the protocol. They include known contraindications for lopinavir/ritonavir, clinical conditions increasing the risk of adverse events associated with lopinavir/ritonavir, known pregnancy or breast feeding, known to be a prisoner, inability to comply with study procedures, and inability to provide informed consent or complete daily symptom surveys in English or Spanish during the two-week observational period.

6.3 Randomization and Blinding

Eligible patients will be randomized in a 1:1 ratio to the intervention arm (lopinavir/ritonavir) or the control arm (placebo). Randomization is stratified by site and age (≥ 65 years versus < 65 years) and uses permuted small block randomization. Patients, treating clinicians, trial personnel, and outcome assessors are blinded to group assignment. Only the investigational pharmacy (who is distributing study medication), the Data Coordinating Center (who is managing the randomization systems including generating the randomization sequence), and one member of the statistical team (who is preparing closed DSMB interim reports) are unblinded.

To maintain the blind, study medication is dispensed with packaging and labelling that does not indicate whether the drug is a placebo or active treatment. Unblinding will occur only if required for subject safety or treatment at the request of the treating clinician and will be done by the

Investigational Pharmacy.

6.4 Timing of study procedures and outcomes assessments

The day of randomization is defined as Baseline and the receipt of the study drug is defined as “Study Day 1”. It is possible for it to take up to two days for study medications to arrive at a participant’s home. For the purposes of analysis, Study Day 1 will be counted as the day on which study medications are received by the participant. To ensure symptoms are assessed daily while on study, and to ensure the primary outcome can be measured through Study Day 15, symptoms are collected daily from the day following randomization to sixteen days following randomization. The symptoms assessed on Study Day 1 (day of receipt of medication) to Study Day 15 are included in the measurements for this trial. At Study Day 15, the primary outcome is assessed. At Study Day 29, additional outcomes are assessed.

7 Sample Size

This study is designed to be analyzed using a Bayesian approach, accepting the possibility of adaptations or sample size adjustments as the trial progresses. Although the design as detailed is Bayesian in nature, a frequentist sample size and target power are provided for consistency with FDA guidance and recommendations. To provide a sample size estimate, we calculated a sample size of 540 patients equally distributed among study arms is needed to have 90% power to detect an odds ratio of 1.75 or greater assuming a traditional proportional odds model and a type I error of 0.05, as proposed by Whitehead (1993). Accounting for an approximate 10% loss to follow-up rate, we plan to enroll 600 patients

An example of the difference between study arms resulting in such an odds ratio is shown in the table. This is based on recommendations from the World Health Organization for COVID-19 Master Protocols that were in place at the time this study was designed

Category	Placebo Arm Proportion	Treatment Arm Proportion
1-Death	1%	0.6%
2-Hospitalized on mechanical ventilation or ECMO	3%	1.8%
3-Hospitalized on supplemental oxygen	4%	2.4%
4-Hospitalized not on supplemental oxygen	3%	1.9%
5-Not hospitalized with symptoms and limitation in activity	10%	6.6%
6-Not hospitalized with symptoms but with no limitation in activity	24%	18.7%
7-Not hospitalized without symptoms nor limitation in activity	55%	68.1%

8 General Analysis Considerations

Here, we describe overarching guidelines that will be followed in the statistical analysis of the TREAT NOW study. The timing and scope of each analysis, the analysis datasets, the approach to handling

missing data, covariate adjustment, subgroup analysis and stopping guidelines are provided. In subsequent sections, the approach to describing the data and modeling the outcomes of interest are described.

8.1 Timing of Analyses

The final analysis will be performed after all subjects enrolled have completed their Day 29 data collection or dropped out prior to their Day 29 data collection, and data are declared query free. Interim analyses are detailed below for safety, efficacy, and futility and will be performed for the primary outcome based on a database pull for interim analyses. At conclusion of the trial and after resolution of all queries, the database will be locked.

8.2 Analysis Populations

The analysis populations are defined below. A participant's inclusion or exclusion status with regard to each analysis population will be set prior to breaking the blind for final analyses based on the criteria as outlined.

8.2.1 Intention to Treat Population

- All subjects who have receipt of study drug (Study Day 1) based upon their randomized allocation.
- Given the study design whereby patients are shipped study drug from a central pharmacy, there might be times when the drug does not get delivered to the patient. In these rare instances the patient will be excluded. All other subjects will be included, and they will be analyzed according to which group the patient was assigned. Thus, the intent to treat (ITT) analysis set includes all subjects who were randomized and received the study drug at their provided address.

8.2.2 Per Protocol Population

- All subjects who receive study drug, report taking at least one dose, and who complete their Study Day 15 survey will be included in the per protocol population.
- Patients will be classified according to the treatment they received with confirmation of receipt from the study pharmacy.

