## **4. STUDY INTERVENTIONS**

### **4.1 Treatment of Study Participants**

A summary of the trial’s schedule of events is included in Appendix A.

Timing of study procedures is based on the time of randomization, which is defined as “Time 0”. Study Day 1 is defined as the day of receipt of the first dose of study drug. We will assess the primary outcome on Study Day 15, which corresponds to 14 days (2 weeks) after the initiation of study drug.

A research physician will prescribe a study medication that a central pharmacy (Belmar Pharmacy) will fill at no charge to the patient and will arrive through overnight mail (typically next day by 10:00AM). The study medication will arrive in blinded blister packs labelled as lopinavir/ritonavir or placebo with the appropriate daily instruction for administration. The goal is initiation of treatment within one day of randomization (Study Day 1).

On Study Days 1-15, the patient will complete brief electronic data collection form through a secure electronic platform that will confirm receipt and administration of study drug and document the number and reason for any missed doses. For those with missing electronic data, telephone follow-up will provide an additional opportunity to clarify study drug administration, as needed. If the participant is hospitalized prior to completion of the study medication, an attempt will be made to continue study medication. However, study medication may be discontinued if felt necessary by the treating clinician in consultation with the local investigator. Unblinding will occur only if required for subject safety or treatment at the request of the treating clinician.

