Important potential risks include PR prolongation at therapeutic dosing, and QT prolongation with supratherapeutic doses. Lopinavir/ritonavir interacts with several drugs since it is an inhibitor of the P450 isoform CYP3A and is likely to increase the plasma concentration of drugs that are metabolized by CYP3A4. Therefore, LPV/r should not be co-administered with drugs primarily metabolized by CYP3A and for which elevated plasma concentrations are associated with serious and/or life-threatening events. A list of such products is included in the lopinavir/ritonavir label. Rare reports of second- or third-degree atrioventricular block in patients with underlying structural heart disease and pre-existing conduction system abnormalities, or in patients receiving drugs known to prolong the PR interval such as verapamil, have been reported in patients receiving lopinavir/ritonavir. Lopinavir/ritonavir should be used with caution in such patients. In addition, QT prolongation with supratherapeutic doses and when lopinavir/ritonavir is co-administered with drugs known to prolong the QT interval has been reported. Because lopinavir/ritonavir is principally metabolized by the liver, caution should be exercised when administering this drug to patients with impaired hepatic function. Extra monitoring is recommended when diarrhea occurs. The relatively high frequency of diarrhea during treatment with lopinavir/ritonavir may compromise the absorption and efficacy (due to decreased compliance) of lopinavir/ritonavir or other concurrent drugs. Serious persistent vomiting and/or diarrhea with lopinavir/ritonavir use might also compromise renal function. The safety of lopinavir/ritonavir for treatment of patients with COVID-19 disease is unknown. COVID-19 may be associated with cardiac effects. lopinavir/ritonavir may prolong QT at supratherapeutic doses and prolong PR at therapeutic doses, resulting in arrhythmias.

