5.2 Treatment arms

The active treatment arm of lopinavir/ritonavir (LPV/r) consists of standard dosing with 400mg/100mg taken orally twice daily for 28 doses. Medication dose packs contain all 28 doses labelled by study day. The LPV/r dosing is based upon extensive PK/PD study evaluations in healthy and HIV+ subjects.

The control arm consists of unmatched placebo taken orally twice daily for a total of 28 doses. Medication dose packs will contain all 28 doses labelled by study day. Given the unmatched placebo pill to LPV/r, exclusion will be exercised to ensure two individuals from the same household are not enrolled in the study and that telephone assessments during the study avoid discussion of the appearance of the study medication.

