9.4 Treatment compliance, protocol deviations and protocol violations

Major protocol deviations and violations will be described. Adherence to the schedule for taking study medications will be reported. Major protocol deviations that will be reported are failure of participant to adhere to the study medication schedule, errors in shipping and handling of study medication including shipping the incorrect medication, and other protocol deviations deemed by the study executive committee to affect the overall integrity of the data. Any such determination will be made before unblinding to treatment arm.

10 Efficacy Analyses

All continuous and categorical variables will be summarized as described previously. The analytic approach is Bayesian with results presented as credible intervals and posterior probabilities for specific hypotheses as defined in the following sections unless otherwise noted.

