10.1.1 Secondary Analyses of Primary Efficacy Endpoint

We will replicate the primary analyses using the per protocol dataset and the safety dataset.

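### The per-protocol set keeps participants who have the dosing deviation that the SAP calls major, so its agreement with ITT would not show robustness to non-adherence

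*SAP*

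**What the plan says.** SAP 8.2.2 sets the entry rule: "All subjects who receive study drug, report taking at least one dose, and who complete their Study Day 15 survey will be included". Participants in this set are classified by treatment received. The course is 28 doses (SAP 5.2: "Medication dose packs contain all 28 doses labelled by study day").

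SAP 8.2.3 uses the same threshold of one reported dose for the safety set. SAP 8.2.1 requires only delivery of study drug for ITT. SAP 8.2 fixes membership of each set before unblinding, by the criteria as written.

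SAP 9.4 treats poor adherence as serious: "Major protocol deviations that will be reported are failure of participant to adhere to the study medication schedule". What it plans is description: "Adherence to the schedule for taking study medications will be reported". It links these deviations to no analysis set.

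SAP 10.1.1 gives the use of the sets: "We will replicate the primary analyses using the per protocol dataset and the safety dataset". Protocol 4.1 shows that dose data exist, since the daily form is to "confirm receipt and administration of study drug and document the number and reason for any missed doses". Neither document plans another efficacy analysis based on adherence.

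**The concern.** A reader expects a per-protocol result to describe people who broadly followed the regimen. Under SAP 8.2.2 a participant can stop after the first dose, complete the Day 15 survey and count as per protocol, while also being listed under SAP 9.4 as a major deviator.

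On adherence the three sets form a very short ladder: drug delivered (ITT), one dose reported (safety), one dose reported plus a survey (per protocol). The survey does not measure adherence. If the three estimates agree, a report could present this as robustness to non-adherence, although the sets were hardly separated on it.

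The protocol gives reason to care. Section 4.2 says that twice-daily dosing needs 3 to 4 days to approach steady state. Section 9.1.2 lists gastrointestinal disorders among the most frequent reactions and warns that diarrhea on this drug may lower compliance and, with it, efficacy. Such non-adherence could fall mainly in the active arm.

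**Working it through.** **Comparison of the sets**

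| Set | Drug delivered | Doses reported | Day 15 survey | Dosing deviators removed |
|---|---|---|---|---|
| ITT (SAP 8.2.1) | yes | none required | no | no |
| Safety (8.2.3) | yes | at least 1 | no | no |
| Per protocol (8.2.2) | yes | at least 1 | yes | no |

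Minimum exposure for the per-protocol set: 1/28 = 3.6%.

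**The plan's own figure.** SAP 7 gives N = 540 for 90% power at an odds ratio of 1.75 and type I error 0.05, by Whitehead's method. Inputs are the placebo proportions in SAP 7 (1, 3, 4, 3, 10, 24, 55%) and the active-arm proportions implied by an odds ratio of 1.75 (category 7: 68.1%). The SAP does not state sidedness. With two-sided 0.05:

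N = 12(1.960 + 1.282)² / [(ln 1.75)² × (1 − Σp̄³)]

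Here p̄ is the mean of the two arms' proportions in each category, (1.960 + 1.282)² = 10.507 before rounding of the quantiles, (ln 1.75)² = 0.3132 and Σp̄³ = 0.2438. So N = 12 × 10.507 / (0.3132 × 0.7562) = 532, close to 540. Power at 540 is 90.4%, and 540/0.90 = 600. The plan's figures reproduce.

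**Dilution illustration.** Assume that a share f of the active arm takes too little drug to have any effect and so has the placebo distribution, that adherers have a true odds ratio of 1.75, and that the share f meets the entry rules of all three sets. The active-arm distribution becomes (1 − f) × adherers + f × placebo. A common odds ratio is then fitted by maximum likelihood and power recomputed as Φ(√[N(1 − Σp̄³)/12] × ln OR − 1.960).

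| f (assumed) | Apparent OR | Power at N = 540 | N if f is removed from both arms | Power there if OR is 1.75 |
|---|---|---|---|---|
| 0% | 1.75 | 90% | 540 | 90% |
| 10% | 1.65 | 83% | 486 | 87% |
| 20% | 1.55 | 73% | 432 | 83% |
| 30% | 1.46 | 61% | 378 | 78% |
| 40% | 1.38 | 48% | 324 | 72% |

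Hand check at the top category:
- f = 20%: 0.8 × 68.1 + 0.2 × 55 = 65.5%, and (65.5/34.5)/(55/45) = 1.55.
- f = 40%: 0.6 × 68.1 + 0.4 × 55 = 62.9%, and (62.86/37.14)/(55/45) = 1.38.

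The present per-protocol set does not remove the share f on grounds of adherence, so it inherits the dilution. The last column assumes that removal introduces no selection bias, which cannot be guaranteed. Power is only a yardstick here, since the SAP attaches no success criterion to this set.

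**The case against.** The definition is lenient, but it is explicit and fixed before unblinding. A reader might infer that SAP 8.2.2 contradicts SAP 9.4. It does not: 9.4 promises to describe major deviations, not to exclude anyone. This stands, and leaves a mismatch between the set's name and its content rather than two conflicting rules.

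A reader might also infer that agreement of the three analyses is guaranteed. That goes too far. The sets differ by participants who report no dose, by those without a Day 15 survey (SAP 7 allows about 10% loss to follow-up) and by any dispensing errors. Only the weak separation on adherence is established.

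Nor would a null result be unreadable. Adherence is to be reported (SAP 9.4), and discontinuation for adverse events or side effects is to be summarised (SAP 11.1). These outputs help to show whether the drug was taken, but they do not estimate its effect in those who took it.

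Protocol 4.6 permits study drug to be stopped in several circumstances, so a low dose count is not always a deviation. This stands and must be handled in any new definition. So does the objection that selecting on adherence happens after randomisation and may act differently by arm, so a stricter set would not cleanly separate an inactive drug from an untaken one.

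Finally, the low-exposure share is assumed, as is zero effect in partial takers. The illustration uses a single-day distribution, whereas the primary model is longitudinal with a treatment-by-time interaction (SAP 10.1).

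**Conclusion.** The point holds as a matter of definition. The set called per protocol applies one-dose exposure and a survey condition, keeps participants with a deviation that SAP 9.4 names as major, and is close to the safety set. Agreement of the three analyses should not be reported as robustness to non-adherence.

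The size is illustrative: about 1.55 to 1.38 in place of 1.75 if 20% to 40% of the active arm has no effect from low exposure. If adherence proves high, the present set would approximate adherers, but nothing in its definition ensures this.

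The survey condition adds a smaller problem. Read literally, it removes participants who die before Day 15, although SAP 8.4 says that the model can be used with missing days.

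A reader might infer that the trial's main conclusion is at risk. The documents do not support that: the primary analysis uses ITT (SAP 10.1), and no stopping rule in SAP 8.5.4 refers to the per-protocol set. This is an inexpensive improvement to a supportive analysis.

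**What to change.** Before unblinding, amend SAP 8.2.2 and 10.1.1 as follows.

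- Rename the present set 'treated set with Day 15 survey'.
- Define the per-protocol set by a fixed adherence criterion from the daily dose data and by absence of the SAP 9.4 medication-schedule deviation. State the threshold in advance; 80% of the 28 planned doses is only an example and has no basis in the documents.
- State how stops permitted by Protocol 4.6 are classified. Do not count early stoppers as adherent merely because no further doses were due, since that would return much of the low-exposure group to the set.
- State how deaths before Day 15 are classified, and do not drop them for lack of a survey. A fixed denominator of 28 doses would also exclude early deaths on dose count, so the rule has to be explicit.
- Label the analysis supportive only, with a caveat that selection after randomisation may differ by arm.

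The cost is SAP wording; no new data are needed. The downside is a smaller set (432 of 540 at f = 20%, 324 at 40%) and the selection risk just named.

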4.1 Preface

Effective therapies for COVID-19 are urgently needed. Lopinavir/ritonavir (Kaletra), an antimicrobial agent used to treat HIV-1, has demonstrated in vitro inhibition of SARS-CoV-2, the virus that causes COVID-19. Initial clinical data have suggested possible relevance as a therapeutic agent when administered early in the disease course of patients with COVID-19. The TREAT NOW study was designed to test the hypothesis that lopinavir/ritonavir reduces disease progression and improves clinical status measured using a seven point at day 15 following receipt of study drug when compared with placebo. The TREAT NOW study is a multicenter, blinded, non-matching placebo-controlled, randomized clinical trial to evaluate the superiority of active therapy (lopinavir/ritonavir) versus placebo control. Briefly, patients testing positive for SARS-CoV-2 infection in an outpatient setting are contacted by research coordinators and invited to participate. Adults with a positive SARS-CoV-2 test are either self-referred or identified via review of testing records at participating sites. Patients who are still symptomatic and who are within six days of symptom onset are invited to participate. Eligible participants who provide their consent to participate using an electronic system undergo comprehensive baseline data collection via phone survey, the participant is randomized, and study drug or placebo is shipped overnight to the participant's home. The participant then completes a daily web-based medication adherence, symptom burden, and hospitalization survey for sixteen days. Missed surveys result in telephone follow up to complete missing data and to re-engage the participant in completing the study. At day 15, the primary outcome is assessed. Patients are followed up once more at 29 days

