5.3 Endpoints/Outcomes

In this section endpoints/outcomes are described with how they should be operationalized for analysis. Additional information on the study population(s) are defined in Section 8.2 with respect to those included for analysis. Per the protocol, timing of study procedures is based on the time of randomization, which is defined as Baseline. Study Day 1 is defined as the day of receipt of the first dose of the study drug.

Primary outcome:

The primary outcome is the daily status based on the proposed Modified COVID Ordinal Outcomes Scale from Study Day 1 through Study Day 15:

1. Death
2. Hospitalized on mechanical ventilation or ECMO
3. Hospitalized on supplemental oxygen
4. Hospitalized not on supplemental oxygen
5. Not hospitalized with symptoms and limitation in activity
6. Not hospitalized with symptoms but with no limitation in activity
7. Not hospitalized without symptoms nor limitation in activity

Each daily status is derived primarily from the daily study survey through day 16 after randomization and the chart review on day 29 after randomization. This is a longitudinal measure of the ordinal outcome from receipt of study medication (Study Day 1) to completion of study treatment (Study Day 15).

Secondary outcomes:

The secondary outcomes are described below with details on operationalization:

- Modified COVID Ordinal Outcome Scale on Study Day 8
 - The ordinal outcome of the previously defined scale on Study Day 8 after one week of treatment.
- Modified COVID Ordinal Outcome Scale on Study Day 15
- Modified COVID Ordinal Outcome Scale on Study Day 29
 - The ordinal outcome of the previously defined scale on Study Day 29 after one month of treatment receipt.
- Proportion of patients hospitalized through Study Day 29
 - A dichotomous indicator if the participant was hospitalized at any point through Study Day 29 as reported on daily surveys or through the Day 29 Chart Review.
- Time to hospitalization through Study Day 29
 - The number of days from receipt of study medication (Study Day 1) to first

hospitalization for any reason through Study Day 29.

- Time to symptom resolution through Study Day 29

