8.2.3 Safety Population

- All subjects who received any study treatment (including control) and reported taking at least one dose but excluding subjects who drop out prior to receipt of the study drug. In the unlikely case a participant receives the incorrect study drug, patients will be grouped according to the treatments that they received in any safety analyses. If a participant receives both placebo and active treatment, they will be considered as receiving active treatment.

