8.4 Missing Data

Missing outcome data for an analysis population will be imputed when necessary using multiple imputation. Outcomes using the Bayesian longitudinal proportional odds model, which includes the primary outcome, will not use imputation since the model facilitates smoothing over missing responses (i.e., the model can still be used even if a participant has missing day(s) of response data). Data on age, gender, race/ethnicity, comorbidities, and duration of acute respiratory infection prior to randomization should not be missing as they are collected as part of enrollment, however imputation procedures will be used in cases of missing values.

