9.3 Derived variables

This study involves several derived variables, such as body mass index and the seven-level ordinal outcome scale. During the data collection process, each component of the derived variable is collected and the first stage in data analysis will be to generate and validate the derived variable. Depending on the distribution of the seven-category modified COVID-19 ordinal outcomes scale, certain categories may need to be combined based upon few or no events.

The primary outcome through Study Day 15 will be derived primarily through the daily surveys (from Days 1 to 16 post-randomization) and supplemented by the Study Day 29 Chart Review to verify details about hospitalization or other healthcare encounters recorded. The method for derivation of other variables not described will be clearly articulated in the analysis report if needed.

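### The per-protocol set requires a completed Study Day 15 survey with no exception for death, so early deaths drop out of the per-protocol replication of the primary analysis

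*SAP*

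**What the plan says.** SAP 8.2.2 sets three conditions for the per-protocol population: receipt of study drug, and that participants "report taking at least one dose, and who complete their Study Day 15 survey will be included in the per protocol population". SAP 8.2 says that membership of each population "will be set prior to breaking the blind for final analyses based on the criteria as outlined". Neither section mentions death.

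SAP 10.1.1 gives the use of the set: "We will replicate the primary analyses using the per protocol dataset and the safety dataset". The primary outcome (SAP 5.3) is the daily seven-level status from Study Day 1 to Study Day 15, with death as level 1. Each status is "derived primarily from the daily study survey through day 16 after randomization and the chart review on day 29"; SAP 9.3 adds that the surveys are "supplemented by the Study Day 29 Chart Review to verify details about hospitalization or other healthcare encounters recorded".

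Three other provisions bear on the point:
- The safety population (SAP 8.2.3) is "All subjects who received any study treatment (including control) and reported taking at least one dose", with no Day 15 survey condition.
- SAP 8.4 says of the longitudinal model that "the model can still be used even if a participant has missing day(s) of response data".
- SAP 4.1 says "Missed surveys result in telephone follow up to complete missing data". Protocol Section 6 adds text messaging that can be used in hospital, and telephone contact triggered by hospitalization. Protocol 5.1 allows an alternate contact as a source of in-hospital outcome data.

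**The concern.** A participant who dies before the Day 15 survey cannot complete it by any route. Followed as written, the rule therefore removes that participant and every daily status recorded before the death. The set is then defined in part by the worst level of the outcome being analysed, and the replication estimates a treatment effect among people who were alive and responded on Day 15.

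The stake is the meaning of this one sensitivity analysis. If the arms differed in deaths before Day 15, in either direction, the per-protocol estimate could not reflect it. A reader comparing it with the ITT result might take agreement or disagreement as information about adherence, when part of it comes from the selection.

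**Working it through.** **1. What the text does to deaths.** SAP 8.2.2 needs a completed Day 15 survey, and SAP 8.2 ties membership to the written criteria. No section counts death as completion. SAP 9.2 lists death among the reasons for dropping out, and SAP 5.3 gives death an explicit value for the free-days endpoints, but 8.2.2 has no matching rule. Level 1 is thus essentially empty over Days 1–15 in this set. The one exception would be someone who completes the Day 15 survey and dies later that day.

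**2. The plan's own figure.** The planning table was first checked against the stated sample size. Inputs from SAP Section 7: odds ratio (OR) 1.75, power 90%, type I error 0.05 (two-sided assumed), and the two columns of category proportions. With p̄ the mean proportion per category, Whitehead's formula is

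N = 12(z₀.₉₇₅ + z₀.₉₀)² / [(ln OR)² (1 − Σp̄³)]

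= 12(1.960 + 1.282)² / [0.5596² × (1 − 0.2435)] = 532.

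The SAP states 540, within 3%, and 540/0.9 = 600. The table is therefore a fair basis for sizing the effect.

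**3. Number lost, at 300 per arm.**
- Deaths: 300 × 1% = 3.0 on placebo and 300 × 0.6% = 1.8 on active, about 5 of 600.
- Deaths plus everyone ventilated or on ECMO, if none of the latter could respond (assumed): 300 × 4% = 12.0 against 300 × 2.4% = 7.2.
- Deaths plus all hospitalized, the extreme: 300 × 11% = 33.0 against 300 × 6.7% = 20.1.

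**4. Effect on the odds ratio.** The common OR is the maximum-likelihood proportional odds estimate on the table's proportions, 300 per arm. The treatment column sums to 100.1% and was rescaled. The standard error (SE) of the log OR with everyone is 0.165. Shift = (log OR with everyone − log OR after removal) / 0.165.

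| Removed | OR | Log OR | Shift |
|---|---|---|---|
| Nobody | 1.739 | 0.5533 | – |
| Deaths | 1.734 | 0.5502 | 0.02 SE |
| Deaths and 10% of categories 2–4 (assumed) | 1.728 | – | 0.04 SE |
| Deaths and 25% of categories 2–4 (assumed) | 1.720 | – | 0.07 SE |
| Deaths and 50% of categories 2–4 (assumed) | 1.704 | – | 0.12 SE |
| Deaths and 75% of categories 2–4 (assumed) | 1.686 | – | 0.19 SE |
| All of categories 1–4 (extreme) | 1.664 | 0.5093 | 0.27 SE |

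Only the deaths row rests on the documents alone. They give no survey loss among the hospitalized.

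**5. Could it hide a mortality difference?** Assumed illustration: placebo as in the table, and active with 3% deaths instead of 1% (9 against 3), the other six categories rescaled in proportion. With everyone the OR is 0.93. Without deaths the two remaining distributions are identical, so the OR is exactly 1.00.

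All of these are Day 15 cross-sections, not results of the longitudinal model.

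**The case against.** The strongest reply is materiality. No decision rests on the per-protocol replication, and the safety-set replication keeps the deaths, so comparing the two would show most of what the condition does. The documented shift is 0.02 SE. All of this stands, and it limits the point to a minor one.

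A second reply is that the survey condition has a purpose. The per-protocol and safety sets both need receipt of drug and at least one reported dose, and both group by treatment received. The Day 15 survey is the main thing that separates them. Asking for an end-of-treatment assessment is a defensible per-protocol choice. This also stands: the model's tolerance of missing days does not make the condition pointless. The defect is only that death cannot satisfy it.

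A reader might infer that hospitalized or severely ill participants drop out of this set as a group. The documents do not support that. Telephone, text and in-hospital completion are provided for, and anyone hospitalized earlier who completes the Day 15 survey stays in with all the earlier hospital days. Those who could not respond by any route may number zero. What the SAP leaves unsaid is whether a report from an alternate contact counts as a completed survey.

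Nor is an empty category a breach in itself: SAP 9.3 already allows sparse levels to be combined. The problem is that the people are removed, not that a level is unused.

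**Conclusion.** The point holds for deaths. As written, 8.2.2 selects on the outcome, and a mortality difference before Study Day 15 could not show in the per-protocol replication. At the planning rates this means about 5 of 600 participants and a change in the Day 15 cross-sectional OR from 1.74 to 1.73 (0.02 SE), slightly toward the null under the assumed benefit. Larger shifts, up to 0.27 SE, need survey losses that the documents do not give and that the follow-up routes make unlikely.

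It would be wrong to conclude that the trial's main result is biased by this rule. The primary analysis uses the ITT set, and the stopping rules, the mortality and hospitalization endpoints and the safety-set replication do not depend on Day 15 survey completion. The conclusion rests on reading 8.2.2 literally. If the sponsor already intends deaths to count, the text should say so, because 8.2 fixes membership on the written criteria. It is worth correcting because it is cheap, not because it is large.

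**What to change.** In SAP 8.2.2, replace the completed-survey condition with one that is met by either:
- death on or before Study Day 15; or
- a Study Day 15 ordinal status known from any source, whether a survey by any route, telephone, an alternate contact or chart review.

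Apply it in the same way to hospitalized and non-hospitalized participants. Waiving the survey only for those who died or were hospitalized would bring in sick non-responders while still excluding mild ones. With an assumed 5–20% loss in categories 5–7, equal in both arms, and categories 1–4 kept, the OR would move from 1.739 to 1.742–1.751. That shift is up to about 0.04 SE, as large as or larger than the one being corrected once the loss reaches 10%.

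The cost is a sentence of SAP text and a little derivation from data already collected, settled before membership is fixed. Some Day 15 statuses may stay unknown, since hospital status depends on access to records or a contact, and chart review alone cannot separate levels 5 to 7 for someone at home. Reporting exclusions from the set by arm and reason would make what remains visible.
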